9.2.2 Annual Reporting to the IRB

The following items will be reported to the University of Maryland IRB in summary at the time of Continuing Review:

- Serious adverse events or deaths that are not related to the research
- All adverse events associated with research including expected AEs Protocol deviations. This includes AEs related to phlebotomy within 48 hours of procedure.
- Serious, continuing, and minor non-compliance
- Any trends or events which in the opinion of the investigator should be reported

9.3 Type and Duration of the Follow-up of Subjects after Adverse Events

All SAEs and non-serious AEs identified in this study will be followed until resolution or until the PI judges the AE/SAE has stabilized and no more follow-up is required. This requirement indicates that the follow-up may be required for some events after the participant discontinues participation from the study. These events will be reported to the IRB annually.

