6.1 Clinical Evaluations	17
6.2 Laboratory Evaluations.....	17
6.3 HCV and HIV Virologic Studies	18
7 Potential Risks and Benefits	19
7.1 Potential Risks.....	19
7.2 Potential Benefits.....	20

TABLE OF CONTENTS

8	Stored Samples and Future Research.....	20
9	Assessment of Safety & Monitoring	21
9.1	Recording/Documentation	22
9.2	Definitions.....	22
9.2.1	Reporting Protocol Deviations, AEs and Deaths	22
9.2.2	Annual Reporting to the IRB.....	22
9.3	Type and Duration of the Follow-up of Subjects after Adverse Events.....	23
9.4	Withdrawal of a Subject.....	23
9.5	Return of Withdrawn/Removed Subjects	23
10	Remuneration Plan for Subjects.....	24
11	Statistical Considerations	24
11.1	Sample size	24
11.2	Description of the Analyses	24
12	Ethics/Protection of Human Subjects	24
12.1	Informed Consent Process	24
12.1.1	Illiteracy and Consenting.....	25
12.2	Subject Confidentiality	25
	Appendix A: Scientific References	25
	Appendix B: Schedule of Procedures/Evaluations	28

List of Abbreviations

AE	Adverse Event/Adverse Experience
Coinfection	Identifier for those with both HIV and hepatitis B or C
DAA	Directly Acting Antiviral
ART	Highly Active Anti-retroviral Therapy
HBV	Hepatitis B Infection
HCV	Hepatitis C Infection
HIPAA	Health Insurance Portability and Accountability Act
MAVERIC	Study short name
IHV	Institute of Human Virology
IRB	Institutional Review Board
N	Number (typically refers to number of subjects/sample size)
PI	Principal Investigator
RT-PCR	Reverse Transcriptase Polymerase Chain Reaction
SAE	Serious Adverse Event/Serious Adverse Experience
SVR	Sustained Virologic Response 12 weeks following therapy
VL	Viral Load
WHO	World Health Organization

Protocol Summary

- Full Title:** **A Pilot Study to Evaluate Anti-HCV Effect of Maraviroc in HIV/HCV Co-infected Patients**
- Short Title:** MAVERIC
- Conducted by:** Institute of Human Virology, University of Maryland
- Principal Investigator:** [name]
- Sample Size:** N= 10
- Accrual Ceiling:** 15
- Study Population:** Adults infected with viral hepatitis C and being treated for HIV infection
- Study Design:** Single-site, longitudinal, open-label, interventional pilot study for evaluation of the effectiveness of Maraviroc on HCV viral levels in patients with HCV and HIV undergoing antiretroviral therapy. Participants will be seen at a IHV Clinic, Baltimore MD 21201.
- Study Duration:** *Start Date:* August 1, 2016
End Date: August 1, 2017.

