3.2 Research Strategy

Study subjects will be selected and enrolled at a single site at IHV. HIV infected participants (coinfected with HCV and DAA-treatment naïve for HCV) who are well controlled on ART will receive Maraviroc for one month and serial measurements of viral and immune parameters will be performed. Rationale for not recruiting treatment naïve HIV/HCV coinfecting participants is based on previous studies that have demonstrated an increase in HCV VL in HIV/HCV coinfecting patients who initiated ART.²⁴ We believe this will interfere from characterizing the anti-viral effect, if any, of CCR5 antagonism. Hence, we plan to do an interventional study with frequent in-vivo viral kinetic analysis to evaluate anti-HCV effect of CCR5 antagonism.

Patients with HIV/HCV coinfection with HIV viral suppression and active HCV infection will be included. Patients will be randomized to one of 2 cohorts: immediate start of maraviroc (cohort 1), and delayed start (cohort 2). All patients will receive 4 weeks of Maraviroc (dose adjusted according to intake of concurrent CYP 3A inducers, see table 1) in addition to their regular ART. The immediate start group will receive maraviroc in addition to their HIV antiretroviral regimen from week 0 to 4. This will be followed by a wash out period of 4 weeks after cessation of Maraviroc. After the 4-week wash out period, patients will be crossed over the no-maraviroc arm. The delayed start group will receive no maraviroc from weeks 0 to 4, followed by a 4 week wash out period, before crossing over to the on-maraviroc arm. Figure 2 below illustrates the study scheme.

[figure not shown]

Figure 2: Study scheme

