5.4 Study visit, immediate start group only: Day 14 (Week 2 visit)

HCV VL will be obtained. Safety assessment will be performed (CBC with differential and CD4 and HIV viral loads. Patient reports of adverse effects). Labs can be completed up to 2 days later.

5.5 Study visits, immediate start group only: Day 21/week 3

HCV VL will be obtained. Labs can be completed 2 days later.

5.6 Study visit, both groups: Day 28/week 4

HCV VL and PBMC, plasma, serum and Paxgene RNA for storage will be obtained. Labs can be completed 2 days later.

Immediate start group: Maraviroc will be discontinued at day 28/week 4.

5.7 Washout period, week 4 through to week 8

5.8 Study visit, both groups: Day 56/week 8

HCV VL and PBMC, plasma, serum and Paxgene RNA for storage will be obtained.

Delayed start group: A review of medical history and medication history will be performed to evaluate for any interim changes from screening visit. Physical exam will be performed. HCV VL and PBMC, plasma, serum, and Paxgene RNA for storage will be obtained. Maraviroc will be started.

5.9 Study visits, delayed start group only: Day 57, 58, 60, 63, 70 (week 10), 77 (week 11)

HCV VL will be obtained

Safety assessment at day 70/week 10 (on week 2 after initiating maraviroc).

Weeks 10 and 11 labs can be completed up to 2 days later.

5.10 Study visit, both groups: Day 84/Week 12

HCV VL and PBMC, plasma, serum. and Paxgene RNA for storage will be obtained. Visits can be completed up to 2 days later.

Delayed start group: Maraviroc will be discontinued. Safety assessment.

Immediate start group: **End of study participation.** Safety assessment.

5.11 Study Visit, delayed start group only: Day 112/week 16

HCV VL and PBMC, plasma, serum, and Paxgene RNA for storage will be obtained. Safety assessment. **End of study participation.** Visit can be completed up to 2 days later.

6 Study Procedures/Evaluations

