- **Disposition at the Completion of the Protocol:** At the completion of the protocol (termination), samples and data will either be destroyed, or after IRB approval, transferred to another existing protocol. Final disposition of any samples cannot be done without written permission from the PI.
- **Reporting the Loss or Destruction of Samples/Specimens/Data to the IRB:**
 - Any loss or unanticipated destruction of samples or data resulting in a violation that compromises the scientific integrity of the data collected for the study will be reported to the IRB.
 - Participants may request at any point not to have their samples stored. In this case, the Principal Investigator will destroy all known remaining samples and report what was done to both the participant and to the IRB. This decision will not affect the subject's participation in any other protocols.

Generally, the results from the research stored samples will not be given to the participant's primary care provider or appear in the medical record. This is because the test results, unlike routine medical testing, may be experimental or preliminary. The relevance of these tests to direct patient care may be unknown. At the participant's request, the results of any research tests will be discussed with the primary care physician by the Investigators.

9 Assessment of Safety & Monitoring

As this is an observational study with intervention limited to blood collection, safety issues are not expected. Only those reportable Adverse Events (AEs) related to the research procedures will be reported. The PI will review the safety data and report any unexpected events to the IRB along with annual continuing review.

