9.2.1 Reporting Protocol Deviations, AEs and Deaths

Anticipated deviations in the conduct of the protocol will not be reported to the IRB unless they occur at a rate greater than anticipated by the study team. Expected adverse events will not be reported to the IRB unless they occur at a rate greater than that known to occur in those having phlebotomy procedures normally. If the rate of these events exceeds the rate expected by the study team, the events will be classified and reported. Deaths related to the natural history of hepatitis or co-infection will be reported at the time of continuing review.

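### IRB reporting rules are written for a blood-draw study: every route with a stated time is annual or at continuing review, although all participants take maraviroc

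*Combined protocol and SAP*

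**What the plan says.** Section 3 calls the study randomized, cross-over and interventional, and section 3.2 states "All patients will receive 4 weeks of Maraviroc". Section 7.1 names serious skin rash, allergic reactions and raised liver tests as possible serious effects of the drug, and says that people with hepatitis B or C co-infection may face more liver problems.

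Section 9 starts from a different description. It treats the study as observational, with blood collection as the only intervention, expects no safety issues, and limits reporting to events related to the research procedures. The reporting rules follow:

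- Section 9: the principal investigator will "report any unexpected events to the IRB along with annual continuing review".
- Section 9.2.1: "Deaths related to the natural history of hepatitis or co-infection will be reported at the time of continuing review".
- Section 9.2.1: expected adverse events are not reported "unless they occur at a rate greater than that known to occur in those having phlebotomy procedures normally". The next sentence adds that events above the rate the study team expects are classified and reported, without saying when.
- Section 9.2.2: unrelated SAEs and deaths, all research-associated adverse events, and trends go into the continuing-review summary. The 48 hours mentioned there defines which phlebotomy events count. It is not a reporting deadline.
- Section 9.3, after naming all SAEs and non-serious AEs: "These events will be reported to the IRB annually".

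The Protocol Summary gives a start date of 1 August 2016 and "End Date: August 1, 2017".

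**The concern.** The safety section and the design section describe two different studies, and the reporting rules follow the wrong one. Yearly reporting may suit a study whose only hazard is a needle stick. It does not suit a trial that adds a drug with recognised serious effects, in patients who may have cirrhosis (section 4.2 admits them; section 4.3 excludes Child-Pugh C).

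Section 9.4 lets the IRB stop the study at any time to protect participants. That power is of use only if information arrives while someone is still to be dosed. If staff follow sections 9 to 9.3 as written, a serious event in an early participant need not reach the IRB until a yearly review, which may come after the last participant has stopped maraviroc.

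**Working it through.** **Step 1. Reporting routes side by side.**

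| Event | Section | Stated time |
|---|---|---|
| Unexpected events | 9 | With annual continuing review |
| SAEs and non-serious AEs | 9.3 | Annually |
| Deaths attributed to underlying hepatitis or co-infection | 9.2.1 | Continuing review |
| Unrelated SAEs and deaths; research-associated AEs; trends | 9.2.2 | Continuing review, in summary |
| Expected AEs above a reference rate | 9.2.1 | None given |

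No row has a prompt deadline. A research-related death has no row of its own and falls under research-associated events.

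**Step 2. Inputs for the timing.** Start 1 August 2016 and end 1 August 2017 (Protocol Summary). In the immediate start group dosing ends on day 28 (section 5.6: "Immediate start group: Maraviroc will be discontinued at day 28/week 4") and the last visit is day 84 (section 5.10). In the delayed start group dosing ends on day 84 (section 5.10) and the last visit is day 112 (section 5.11).

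**Step 3. Planned duration.** 1 August 2017 − 1 August 2016 = 365 days, which equals one annual reporting interval.

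**Step 4. Last possible dosing day if all visits finish on time.** Latest enrolment = study end − last-visit day. Latest dosing day = latest enrolment + end-of-dosing day.

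- Immediate: 1 August 2017 − 84 days = 9 May 2017; + 28 days = 6 June 2017, which is 84 − 28 = 56 days before study end.
- Delayed: 1 August 2017 − 112 days = 11 April 2017; + 84 days = 4 July 2017, which is 112 − 84 = 28 days before study end.

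The last possible dosing day is therefore 4 July 2017.

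**Step 5. First annual report, clock starting on 1 August 2016 (assumption).** It falls on 1 August 2017, after all dosing. For a participant enrolled on the first day, an event on the last dosing day waits 365 − 28 = 337 days (immediate) or 365 − 84 = 281 days (delayed).

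**Step 6. Range for the unknown clock.** The documents give no IRB approval or continuing-review date. If the clock starts k days earlier, the report falls on 1 August 2017 − k. It falls on or after 4 July 2017 only if k ≤ 28. The waits in the last column are 337 − k and 281 − k.

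| k (days) | Report date | Relative to 4 July 2017 | Wait, first-day enrolee (immediate / delayed) |
|---|---|---|---|
| 0 | 1 August 2017 | After | 337 / 281 days |
| 28 | 4 July 2017 | Same day | 309 / 253 days |
| 29 | 3 July 2017 | Before | 308 / 252 days |
| 60 | 2 June 2017 | Before | 277 / 221 days |
| 90 | 3 May 2017 | Before | 247 / 191 days |

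For k of 29 or more, the report precedes the end of dosing only for late enrolees. At k = 60, in the delayed start group, these are participants enrolled after 2 June 2017 − 84 days = 10 March 2017.

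**The case against.** Several points on the other side have force.

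- **The timing is conditional.** A reader might infer that no report can reach the IRB before dosing is over. The documents do not establish that. They give no review date, IRB approval may come well before the start, and an overrun would extend dosing past 4 July 2017. The statement holds only inside the range in Step 6.
- **The annual wording is partly ambiguous.** The sentence in section 9.3 could cover only events still followed after participation ends, the phrasing in section 9 could mean in addition to annual review, and a summary list does not forbid earlier individual reports. This stands as a reading, but no version of it supplies a deadline, and section 9.2.2 still routes events to continuing review.
- **The phlebotomy benchmark is not blind to drug events.** A reader might infer that it hides a drug-related excess. Section 7.1 lists pain, bruising, fainting and rare infection as phlebotomy risks, so a single serious rash would probably exceed a phlebotomy rate. The benchmark is inapplicable rather than insensitive. Putting maraviroc rates in its place could make matters worse by turning liver events into expected ones, and section 7.1 gives no rates to use.
- **The rule on deaths does not cover drug-caused deaths by its terms.** A reader might infer that liver deaths on maraviroc will be held back. That would require a misattribution. What stands is that the label decides the timing, and sections 9 to 9.3 describe no attribution procedure.
- **Oversight is not absent.** Adverse events are monitored weekly on drug (sections 6.1 and 6.2) and recorded immediately (section 9.1), the principal investigator reviews safety data (section 9), and section 9.4 provides for considering discontinuation where acute hepatitis or hypersensitivity is suspected. The gap is in the route to the IRB.
- **IRB policy may already require faster reports.** It is not in the documents. If it does, the protocol should say so, because staff will work from the protocol.

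**Conclusion.** The point holds as a conflict between the safety section and the design, with a practical consequence. Every IRB reporting route with a stated time is annual or at continuing review, and the remaining trigger has no time and a reference rate that does not fit a drug.

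The timed rules require no report before the last possible dosing day, 4 July 2017, on two assumptions: the annual clock starts no more than 28 days before 1 August 2016, and the study keeps to its dates. With a clock 60 or 90 days early, a report could come while late enrolees are still to finish dosing, yet an event at the end of a first-day enrolee's dosing would still wait 191 to 277 days.

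The absolute risk is limited by the planned 10 participants (ceiling 15) and an approved drug, so this should be corrected but does not undermine the trial as a whole. The documents do not support saying that the IRB will certainly learn nothing during dosing.

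**What to change.** Delete the observational premise in section 9 and reconcile sections 9, 9.2.1, 9.2.2 and 9.3 with the interventional design in sections 3 and 3.2.

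- Require individual, prompt reports to the IRB of SAEs, unexpected events and all deaths occurring on or after maraviroc, whatever cause is assigned. State the period in days; the documents give none, so the sponsor should take it from the IRB's requirements.
- Keep annual review as a summary only.
- Confine the phlebotomy-rate rule to blood-draw events. Do not let it, or a substitute expected rate for drug events, delay the report of a serious event.
- State the continuing-review date.

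The cost is an amendment to the wording and a few individual reports among at most 15 participants. Adverse events are already collected weekly on drug, so no new data collection is needed.

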9.4 Withdrawal of a Subject

A participant may withdraw from the study at any time. As part of their duties to ensure that research participants are protected, the IRB, IHV, or other government agencies may discontinue the study at any time. Voluntary withdrawal from the protocol may occur at any time at the request of either the participant or the PI. If a request is made to withdraw from the protocol, all further planned study procedures will be immediately cancelled and further follow-up will be terminated. Samples and data collected prior to this request will be stored and used as outlined in the protocol unless a specific request is made by the participant to remove all of their samples from the study. Data already obtained from the participant's samples will not be discarded. In addition, participants with poor compliance and/or failure to present for follow-up visits may be withdrawn from the study at the discretion of the PI.

If a patient becomes pregnant during the course of the study, the investigator, in consultation with the patient, should consider whether the potential benefit justifies the potential risk to the fetus of continuing the study therapy. If it is determined that the potential benefit does not outweigh the potential risk to the fetus, the patient should be discontinued from the study.

Should a subject develop evidence of HIV virologic breakthrough, or decline in CD4 to less than 200 (if above 200 at baseline) during the study they will be evaluated by their primary HIV provider and may be withdrawn from the study at the discretion of the PI.

Discontinuation of maraviroc will be considered in any patient with signs or symptoms of acute hepatitis, in particular if drug-related hypersensitivity is suspected or with increased liver transaminases combined with rash or other systemic symptoms of potential hypersensitivity (e.g. pruritic rash, eosinophilia or elevated IgE).

Should a subject be started on anti-HCV therapy while in the study, maraviroc will be discontinued and the subject will be withdrawn from the study.

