11.2 Description of the Analyses

We estimate a 1 log drop in HCV VL in seven days is true.

The primary efficacy analysis will be intention-to-treat and include all patients who were enrolled into the study and received at least one dose of the study medication. Demographic and baseline characteristics will be summarized using standard descriptive statistics. Association of adverse events with treatment duration, HIV coinfection, fibrosis stage, and presence of cirrhosis will be explored. A 2-sided, exact, 1-sample binomial test will be used to test the statistical hypothesis described above at a significant level of 0.05. All analyses will be performed on SAS, version 9.3 (Cary, NC) or STATA version 13.0.

12 Ethics/Protection of Human Subjects

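### Section 9.4 allows withdrawal by the PI for poor compliance and then ends follow-up, which undermines the intention-to-treat analysis and conflicts with Section 9.3 on adverse-event follow-up

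*Combined protocol and SAP*

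**What the plan says.** **Who may withdraw a participant.** Section 9.4 states: "Voluntary withdrawal from the protocol may occur at any time at the request of either the participant or the PI". Later in the same section: "participants with poor compliance and/or failure to present for follow-up visits may be withdrawn from the study at the discretion of the PI". No threshold for poor compliance is given, and the text does not say whether it means compliance with maraviroc, with visits, or with both.

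**What happens next.** Under Section 9.4, once a request to withdraw is made, "all further planned study procedures will be immediately cancelled and further follow-up will be terminated". No exception is made for outcome samples or safety. Section 9.5 bars a withdrawn participant from returning.

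**What is kept.** Section 9.4 also says "Samples and data collected prior to this request will be stored and used as outlined in the protocol", unless the participant asks for the samples to be removed, and "Data already obtained from the participant's samples will not be discarded".

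**Adverse events.** Section 9.3 says "All SAEs and non-serious AEs identified in this study will be followed until resolution or until the PI judges the AE/SAE has stabilized", and that "the follow-up may be required for some events after the participant discontinues participation from the study".

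**Analysis.** Section 11.2 says "The primary efficacy analysis will be intention-to-treat" and defines the set as enrolled patients who took at least one dose. Section 11 gives no rule for missing viral loads, no dropout allowance and no sensitivity analysis.

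**The concern.** An intention-to-treat analysis needs outcomes on the people it includes. Here the investigator knows who is taking maraviroc and when, may remove a participant for poor compliance at discretion, and by doing so appears to end that participant's viral load sampling. If maraviroc acts on HCV, poor compliance is plausibly related to a smaller fall in viral load. The missing values could then be informative, and the on-drug estimate would lean towards good adherers. With 10 patients, each one is a tenth of the data.

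Safety is at stake as well. Safety and tolerability form a secondary objective, and HIV breakthrough and changes in CD4 and HIV viral load are secondary endpoints. If follow-up stops at withdrawal, an event that leads to withdrawal may not be followed to its outcome, although Section 9.3 says it should be.

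**Working it through.** The plan gives no figure on this point to reproduce. The main check is a comparison of the text; the arithmetic that follows is illustrative.

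**1. Does termination of follow-up apply to compliance withdrawals?** The termination sentence is triggered by a request to withdraw. The sentence before it names the PI as one possible requester. The compliance sentence comes later and does not repeat the consequence. Applying termination to compliance withdrawals is therefore a reasonable reading, but not an explicit one.

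**2. Section 9.3 against Section 9.4.** Section 9.3 carries adverse-event follow-up beyond the end of participation where needed. Section 9.4 ends follow-up at withdrawal. One could read 9.4 as cancelling only planned procedures and leaving unscheduled adverse-event follow-up open. However, its second clause ends follow-up without qualification, and neither section refers to the other. As written, they conflict.

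**3. Section 9.4 against Section 11.2.** Intention-to-treat fixes who is analysed. Section 9.4 removes no dosed participant from that set and keeps the earlier data. What it stops is later measurement, and Section 11 does not say how the gaps are handled.

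**4. Which endpoints are exposed?** The Protocol Summary puts the primary endpoint at day 7. Sections 5.3 to 5.6 schedule HCV viral load for the immediate-start group on days 0, 1, 2, 4, 7, 14, 21 and 28. Sections 5.8 to 5.10 schedule the matching on-drug days for the delayed-start group (56, 57, 58, 60, 63, 70, 77 and 84).
- A withdrawal before the day 7 on-drug sample (day 63 for delayed start) loses the primary outcome.
- A later withdrawal leaves the primary outcome intact but loses some of the week 2, 3 and 4 values, and possibly the week 2 HIV viral load and CD4.
- Section 11.1 says week 7 instead of day 7. No visit is scheduled then; if week 7 were meant, exposure would be wider.
- The analysis set requires a dose, and delayed-start participants are first dosed on day 56. One withdrawn before then drops out of the set although randomised.

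**5. Worst-case shift in a mean.** Assume 10 independent normal responses and that the weakest are the ones lost. The expected lowest and second-lowest of 10 standard normal values are −1.539 and −1.001. Because the 10 expected values sum to zero, the mean of the rest is:
- lowest one lost: 1.539 / 9 = 0.171 SD;
- lowest two lost: (1.539 + 1.001) / 8 = 2.540 / 8 = 0.318 SD.

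The documents give no SD, so these cannot be turned into log units.

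**6. The planned test.** Section 11.2 names a two-sided exact one-sample binomial test at 0.05 but states no null proportion. Assume a true response of 0.9.

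| Assumed null | Situation | Responders needed | Power |
|---|---|---|---|
| 0.5 | 10 observed | 9 of 10 (p = 0.021) | 0.74 |
| 0.5 | 1 of 10 withdrawn, counted as failure | 9 of 10 | 0.9^9 = 0.39 |
| 0.5 | 2 of 10 withdrawn, counted as failures | 9 of 10 | 0 |
| 0.5 | 9 complete cases | 8 of 9 (p = 0.039) | 0.78 |
| 0.5 | 8 complete cases | 8 of 8 (p = 0.008) | 0.43 |
| 0.1 | 10, 9 or 8 complete cases | 4, 4 or 3 | about 1.0 |

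With a null of 0.5, one withdrawal gives power of 0.39 or 0.78 depending only on how the missing value is treated, which the plan leaves open. With a null of 0.1, losing one or two complete cases hardly matters.

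**The case against.** The strongest reply is that this is narrow. Withdrawal for compliance is optional, earlier samples are kept, and the primary endpoint comes after one week on drug, so few participants are likely to be lost before it. Those withdrawn for not attending already have missing values, whatever Section 9.4 says. Section 9.3 is the specific rule for adverse events and already covers people who have left, so a single cross-reference would settle that conflict. PI discretion over compliance may also be a fair choice in a small kinetics pilot. Most of this stands and limits the size of the point. It does not remove the unqualified end to follow-up or the missing rule in Section 11.

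A reader might also infer stronger things that the documents do not support:
- *That Section 9.4 contradicts intention-to-treat.* It does not: no dosed participant is excluded and no earlier data are dropped.
- *That outcomes of poor adherers are never collected.* They are collected up to withdrawal, and withdrawal is discretionary.
- *That the plan never separates stopping maraviroc from leaving the study.* Section 9.4 considers stopping maraviroc for suspected hepatitis or hypersensitivity without mentioning withdrawal, and for anti-HCV therapy it names both acts. What it leaves unsaid is which visits continue once drug is stopped.
- *That only withdrawal of consent should end sampling.* That would override the provisions in Section 9.4 on pregnancy, anti-HCV therapy, HIV breakthrough and CD4 decline, and the bar in Section 4.1 on research procedures during pregnancy.

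**Conclusion.** The point holds in a limited form. On a reasonable reading, Section 9.4 stops outcome collection when the PI withdraws a poorly compliant participant. In an open-label trial of 10 with no missing-data rule, that undermines the intention-to-treat analysis. The primary day 7 result is exposed only to losses before that sample; the week 2 to 4 viral loads and safety endpoints are exposed for longer. Separately, Sections 9.3 and 9.4 conflict on adverse-event follow-up and must be reconciled.

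The size is not determined by the documents. The shifts of 0.17 and 0.32 SD should not be read as expected bias: they assume that the weakest responders are the ones lost. If maraviroc had no effect on HCV, poor compliance would give no evident reason to select weak responders. They also concern a mean, whereas the planned test is binomial. The power figures rest on an assumed null and response rate and range from a serious loss to almost none.

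**What to change.** 1. **Section 9.4.** State that poor compliance with maraviroc alone does not end data collection. Such participants, if they still consent, keep the HCV viral load and adverse-event visits already scheduled and are analysed in their assigned group.
2. **Section 11.** State how HCV viral loads missing after withdrawal are handled in the primary analysis and in the week 2 to 4 analyses. This rule also covers gaps from missed visits.
3. **Sections 9.3 and 9.4.** Reconcile them so that adverse-event follow-up continues after any withdrawal unless consent for it is withdrawn.

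Leave the provisions on pregnancy, anti-HCV therapy, HIV breakthrough or CD4 decline, and stopping maraviroc as they are, apart from making them consistent with Section 9.3.

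The cost is protocol wording and some staff effort to retain poorly adherent participants. The viral load and adverse-event visits in item 1 are already in the schedule.
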